For this project, we will randomize 80 youth with obesity (13 – 18yrs) and a caregiver (dyads) to the Brenner FIT condition or the Brenner mFIT condition. All participants will complete baseline measures prior to randomization, and at three and six months. All youth participants will receive a commercially available activity monitor. Caregivers will receive podcasts with a story about a caregiver supporting weight loss in a child by providing healthy foods/activities for his/her family, including healthy eating and physical activity information. Children will receive animated videos that contain healthy eating and physical activity messaging, with an engaging story of a child losing weight. All participants will have access to a website and mobile apps where they will track weight, diet, and physical activity for themselves (youth) or their child (parents). Based on their reports of weight, eating, and physical activity, the messaging received from clinical staff by the families will be individually tailored to promote healthy behaviors and overcome perceived barriers. The proposed research is innovative in that it explicitly incorporates theory into the intervention and evaluation components of the project and builds upon an existing literature on mHealth interventions that use mobile technology.

Setting

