Secondary	Diet	Baseline, 3 & 6 months	To assess diet in participating youth, we will use NCI's automated, self-administered 24-hour dietary recall, the Automated Self-Administered 24-hour (ASA24 (registered trademark) dietary assessment tool (version: ASA24-2016) on three, non-consecutive days (including one weekend day).
Secondary	Economic costs of the mHealth intervention costs	Baseline, 3 & 6 months	Clinical costs of the mHealth intervention will be compiled over the duration of the program. Examples include materials (eg, printing of materials for parents, youth, staff), equipment, training costs (eg, hourly wages for employees), and costs for ongoing interactive support (eg, time allocated to social media).

Analytical Plan

	Youth Only Measures
Physical Activity	Physical activity data will be collected using ActiGraph™ accelerometers (Shalimar, FL) currently owned by the team. The accelerometers will be set to collect data in “raw” format and analyzed by converting the data to 1-second epochs to account for the intermittent and sporadic nature of children’s PA and to improve the ability to capture the transitory PA patterns of children. During each 7-day data collection period, these monitors will be affixed to a strap on the subject’s non-dominant hand. This protocol is being employed in NHANES and has been used successfully in studies of PA. ¹⁹⁻²¹ We will distill the cut points in a manner consistent with emerging research ²² that allows for comparability with waist-based estimates. ^{23,24} Participants will be instructed to wear the monitor continuously over the next 7 days except during bathing and sleeping. Participants will also be given activity logs with the monitors ²⁵ and small gifts to encourage compliance. Text messages will be sent on the first morning of monitoring and after the last day of monitoring to encourage compliance and timely monitor return. Once an accelerometer is received, data from the accelerometer will be downloaded using the manufacturer’s software and USB computer interface. We will reduce, clean, and process the accelerometer using custom scripts in Stata as in our previous studies. We have used these strategies effectively in community-based data collection. ^{26,27,28,29,30,31} The accelerometers will be initialized and set to record beginning at 5:00am the day following their distribution. This will provide 7 days of data for analysis, from which we will extract four or more complete

	(>10 hour) days.

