Diet	To assess diet in participating youth, we will use NCI's automated, self-administered 24-hour dietary recall, the Automated Self-Administered 24-hour (ASA24®) dietary assessment tool (version: ASA24-2016) on three, non-consecutive days (including one weekend day). The ASA24-2016 is available on both computers and mobile devices. All youth participants will complete one ASA24 at their baseline orientation, and at 3-month and 6-month follow-up office visits to encourage compliance while allowing youth and caregivers to ask questions and gain comfort with using the system. The project coordinator will contact participants within six days (on a randomly selected day) following the office visits to inform participants that they should complete the second/third dietary recall and will offer to conduct the recall over the phone if the youth need assistance (the ASA24 has been shown to perform equally well as a self-administered or interviewer administered questionnaire). ^{32,33} A series of follow-up reminder messages and/or phone calls will be made by the coordinator to encourage completion of the second/third of the two recalls if not completed within 24-hours following the first contact after the clinic visit.

	Caregiver and Youth Measures

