Physical activity	Y	–	Accelerometry (7 days of monitoring): used to estimate minutes of moderate-to-vigorous physical activity per day
Dietary intake	Y	–	Automated Self-Administered 24-hour (ASA24-2016) dietary assessment tool: used to estimate average daily caloric intake
Autonomy	Y	SDT	Relative Autonomy Index; produces a continuous score
Autonomy support	C	SDT	Motivators' Orientations Questionnaire; produces a continuous score
Behavioral self-regulation	Y	SCT	Effortful control, problem solving, soothability, delay of gratification, and self-reinforcement measured by scales previously validated in adolescents; produces continuous scores for all subscales
Outcome expectations	Y	SCT	Expectations about outcomes of weight loss; produces a continuous score
Relatedness	C/Y	SDT	The relatedness and dependency subscales of the Depressive Experiences Questionnaire: produces a continuous score
Self-efficacy for PA	Y	SCT	Self-Efficacy for Exercise Behaviors; produces a continuous score
Self-efficacy to HE	Y	SCT	Self-efficacy to make healthy food choices; produces a continuous score

*Caregiver/Youth; **SCT**: Social Cognitive Theory^{18,153}; **SDT**: Self-determination Theory^{19,64}; **HE**: healthy eating; **PA**: physical activity

Results will be analyzed initially using descriptive statistics. Comparison between groups will be done using chi square tests for proportions, and t-tests or ANOVA procedures for continuous variables. Regression analysis will be performed to identify independent outcome predictors. Other inferential statistical analysis will be conducted as appropriate.

Human Subjects Protection

Subject Recruitment Methods

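### Does prompting diet recalls 2 and 3 on a random day defeat the requirement for separated days with a weekend day?

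*Combined protocol and SAP*

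**What the plan says.** The Diet row of the Outcome Measure(s) table and the Diet entry of the Analytical Plan (Youth Only Measures) give the same rule. Youth complete the ASA24 "on three, non-consecutive days (including one weekend day").

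The Diet entry then gives the logistics. The first recall is tied to the visit: "All youth participants will complete one ASA24 at their baseline orientation, and at 3-month and 6-month follow-up office visits". For the remaining two, "The project coordinator will contact participants within six days (on a randomly selected day) following the office visits". The stated purpose of this contact is "to inform participants that they should complete the second/third dietary recall". Reminder messages or calls follow "if not completed within 24-hours following the first contact after the clinic visit".

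Table 2 states the purpose of the recalls: "used to estimate average daily caloric intake". The Design section sets the time points: "All participants will complete baseline measures prior to randomization, and at three and six months". Diet is listed as a secondary outcome.

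**The concern.** The measure is defined by two conditions on the calendar, but the sentence that schedules recalls 2 and 3 mentions neither. Read alone, it allows a prompt on the day after the visit, which breaks the spacing, or prompts on weekdays only, which lose the weekend day. It does not say whether one contact covers both recalls or each has its own. The reminders for a late recall do not mention spacing or the weekend either.

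If staff drew days with no restriction, many sets would miss the stated definition. The number of weekend days would then vary by chance from one set to the next. Table 2 states no weekday/weekend weighting, so that variation would pass straight into the mean daily intake compared between arms. With 80 youth and three time points, up to 80 × 3 = 240 assessments are involved.

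**Working it through.** The plan gives no figure to reproduce, so the check is an enumeration followed by a standard-error calculation.

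**Inputs from the documents.** Recall 1 is at the visit (day 0); contact falls in days 1 to 6; three recalls, none adjacent, one on a weekend (Diet entry); 40 dyads per arm (Objectives, Primary Aim 2).

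**Assumptions.** Visits fall Monday to Friday with equal frequency. Prompts are answered the same day. The weekend condition means at least one weekend day. The documents do not say whether the day completed or the day reported (the day before) counts, so both are shown. They also give no kcal SD or weekend effect. I take an SD of 400 to 800 kcal for the three-recall mean and a weekend-weekday difference D of 100 to 400 kcal.

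**Step 1: unrestricted draw of two distinct days.** There are C(6,2) = 15 pairs, so 15 × 5 = 75 sets. Spacing holds for the pairs (2,4), (2,5), (2,6), (3,5), (3,6) and (4,6): 6/15 = 40%. A weekend day is present in 60% of sets (completed) or 68% (reported). Pairs that meet both conditions:

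| Visit day | Mon | Tue | Wed | Thu | Fri | Total |
|---|---|---|---|---|---|---|
| Day completed | 5 | 4 | 4 | 5 | 3 | 21/75 = 28% |
| Day reported | 6 | 5 | 4 | 4 | 5 | 24/75 = 32% |

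Other readings differ. Two draws that may coincide give 42/180 = 23% and 48/180 = 27%. A single contact with recall 3 two days after recall 2 gives 50% to 60%; with recall 3 the next day it gives 0%.

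**Step 2: draw restricted to qualifying days.** The same table shows that every weekday visit leaves 3 to 6 qualifying pairs in the six-day window. The tightest case is a Friday visit on the day-completed basis: Sunday, then Tuesday, Wednesday or Thursday. The random contact and the definition can therefore both be honoured, and compliance is 100% when prompts are answered on the day.

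**Step 3: noise from an unrestricted draw.**
- Day completed: 40% of sets have no weekend day, 53.3% one, 6.7% two. Mean 0.667; variance (0.533 + 4 × 0.067) − 0.667² = 0.356; SD of the weekend share √0.356 / 3 = 0.199.
- Day reported: 32%, 56% and 12%. Mean 0.80; variance (0.56 + 4 × 0.12) − 0.80² = 0.40; SD of the share √0.40 / 3 = 0.211.

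**Step 4: effect on the standard error, taking the larger SD (0.211).** The weekend component of the SE of an arm difference is 0.211 × D × √(2/40). That is 4.7 kcal at D = 100 and 18.9 kcal at D = 400. The rest of the SE is SD × √(2/40): 89.4 kcal at SD 400 and 178.9 kcal at SD 800. Independent components add as squares:
- Largest effect (SD 400, D = 400): √(89.4² + 18.9²) = 91.4, a rise of 2.0 kcal or 2.2%.
- Smallest effect (SD 800, D = 100): √(178.89² + 4.7²) = 178.95, a rise of 0.06 kcal or 0.03%.

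Dropout would scale both components alike and leave the percentages unchanged. The sums are for one time point; a change score would carry the weekend component at both ends.

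**The case for a change.** The strongest case is that a definition needs a procedure that delivers it. Staff who follow the scheduling sentence to the letter would draw any day, and nothing in the text would show that a set had missed the spacing or the weekend. Good intentions also do not cover lateness. Among schedules that qualify at the outset, if recall 2 slips by one day only 7/21 (33%) to 10/24 (42%) still qualify; if recall 3 slips, 15/21 (71%) to 18/24 (75%) do. The plan does provide reminders for a late recall, but they carry no check on the calendar. Reduced caloric intake is a stated target of the intervention (Primary Aim 1), so the measure is not incidental.

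Part of this stands. The text leaves open how many contacts are made, which day counts and where a late recall should move. A line in the coordinator's working instructions would settle all three. But the compliance percentages describe a draw that ignores the rule opening the same paragraph. They do not forecast what staff will do. The arithmetic also depends on weekday visits and same-day answers, which the documents do not establish; the Participant Interaction section even allows assessments outside the clinic. Bias between arms would arise only if late or missed recalls differed by arm, and the random draw does not cause that.

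**Conclusion.** No change to the plan follows. The plan states the measure it wants, and the contact step can be carried out within it for any weekday visit. What is missing is scheduling detail that a coordinator reading the whole Diet entry would fill sensibly, by drawing at random among qualifying days. If that were not done, the cost would be extra noise common to both arms. At a single time point the standard error would rise by about 0.03% to 2.2%, given the assumed SD of 400 to 800 kcal, the assumed weekend difference of 100 to 400 kcal, Monday-to-Friday visits and two distinct days. Diet is a secondary outcome of an 80-dyad pilot about acceptability and feasibility, and the documents rest no power claim on it. No result or conclusion would change.

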Adolescents under the age of 13 will be excluded. Caregivers, who are not between the ages of 30-60 years old will also be excluded. If participants do not have access to a smartphone or tablet, they will not be able to participate.

- **Sample Size**

80 dyads which consist of youth and caregiver pairs.

Interventions and Interactions

Conditions	
Control condition: Brenner FIT (ie, standard	After referral, families attend an orientation, in

care)
	
which they are then scheduled for an initial introductory 2-hour intake group session and cooking class; these occur within 2-4 weeks of the orientation. Monthly 1-hour long visits with the dietitian, counselor, and PA specialist are held for 6 months, in which the child and caregiver see the pediatrician. During the 6 months of treatment, they attend 4 group classes, choosing from topics such as meal planning, PA, and parenting. Specialized visits with the PA specialist or dietician are scheduled as pertinent issues arise. Clinic visits include individualized goal setting (for behaviors family/clinician have jointly agreed to address), healthy eating and physical activity education, and behavioral counseling to implement changes at home. Motivational interviewing, modified by Brenner FIT for use with families, 5 is the key to treatment; family counselors are trained in cognitive behavioral therapy, parenting support/mindfulness, and employ these approaches to assist families in developing healthy habits. Self-monitoring is part of the treatment, using hand-written, paper diet and PA logs, completed by parents and children and returned to clinicians. Brenner FIT is successful in enrolling families into research studies, including African Americans and Latinos.^{6,7,8,9} Brenner FIT sees ~200 new patients/families per year; ~66% of those enrolled successfully lose weight. The children who are successful display a decrease in BMI z-score of 0.07 to 0.1, with an average BMI z score decrease at 8 months of 0.11. A .1 - .15 decrease in BMI z-score is linked with healthy changes in cardiometabolic biomarkers.^{10,11}

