	
determination Theory and Social Cognitive Theory including: 1) observational learning, 2) outcome expectations, 3) autonomy, and 4) relatedness. Like the podcasts, the videos will be accessible from the mobile-enabled website and sharable via social media once released for viewing.
 
Component 5: Participants will be encouraged to follow each other and a curated list of health professionals on MealLogger. These interactions will be encouraged during Brenner FIT group sessions. Our team has extensive experience with developing and evaluating social media messages for support during weight loss. In a previous weight loss intervention that used Facebook for social support, we found that messages that were framed as polls or requests for suggestions from the group garnered the most interaction.¹⁸
 
Component 6: Tailored feedback will be provided by clinical staff based upon reports generated from self-monitoring data. Clinical staff will receive a weekly report for each adolescent patient that will be given a quick summary of the level of self-monitoring, nutritional content of recorded meals, level of physical activity engaged in, and progress on behavioral/weight loss goals. Staff will then use this information to engage with dyads via face-to-face meetings, direct texts, and emails to give feedback based upon behavioral progress, encouragement to engage in greater self-monitoring, and/or theoretically informed messages to promote self-efficacy, positive outcome expectations, and self-regulatory behaviors.

--	---

Outcome Measure(s)

Type	Name	Time Frame	Brief Description
Primary	BMI z-score	Baseline, 3 & 6 months	Weight status of caregivers and youth will be quantified through calculation of BMI derived from measurement of height and weight at the intake and follow-up visits. Both height (plus/minus 0.1 cm) and weight (plus/minus 0.5 kg) will be recorded twice and values will be averaged to produce the final value using a Tanita(registered trademark) digital scale and a Seca(registered trademark) Height Rod (respectively). BMI will be calculated as kg /m ² . BMI z-score will be calculated using CDC growth charts.
Secondary	Physical activity	Baseline, 3 & 6 months	Physical activity data will be collected using ActiGraph (trademark) accelerometers worn continuously over 7 days except during bathing and sleeping.

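### Youth BMI z-score, the outcome typed Primary, has no baseline-adjusted comparison; naming ANCOVA at 6 months is a free, modest improvement

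*Combined protocol and SAP*

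**What the plan says.** The Outcome Measure(s) table types BMI z-score as Primary, with baseline, 3 and 6 months as its times. The variable is defined: "BMI z-score will be calculated using CDC growth charts". The same row covers both members of the dyad: "Weight status of caregivers and youth will be quantified through calculation of BMI".

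The statistical text is the short paragraph after Table 2 in the Analytical Plan. After a sentence on descriptive statistics it reads: "Comparison between groups will be done using chi square tests for proportions, and t-tests or ANOVA procedures for continuous variables". Two sentences follow: "Regression analysis will be performed to identify independent outcome predictors" and "Other inferential statistical analysis will be conducted as appropriate".

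The Design section places baseline before allocation: "All participants will complete baseline measures prior to randomization, and at three and six months". Interventions and Interactions gives the length of treatment: "During the 6 months of treatment, they attend 4 group classes".

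No section says whether the follow-up value or the change is compared, which visit is the main one, or whether baseline BMI z-score is a covariate.

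**The concern.** A t-test on the 6-month value and a t-test on the change from baseline both fit the wording. They estimate the same arm effect, but from the same data they give different numbers and different standard errors. The first ignores the baseline value. The second subtracts it in full, whatever the correlation. Adjusting for it as a covariate uses it in the proportion the data support. In expectation that is at least as precise as either alternative, apart from a very small cost of estimating the slope.

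The regression sentence concerns predictors of outcome. It names neither an arm contrast nor a baseline covariate. The closing sentence would allow adjustment but does not promise it.

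At stake are the width and the definition of the pilot's estimate of the arm difference in BMI z-score, which is the figure a reader would carry forward to a later trial.

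**Working it through.** There is no sample-size or precision figure in the plan to reproduce. It gives 80 dyads and no alpha, power, design effect, correlation or dropout.

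**Inputs**
- n = 40 per arm (Objectives, Primary Aim 2).
- SD = 0.5 at each visit. Subjects selection criteria gives BMI z-score 2.6 +/- 0.5, read here as mean and SD. It describes the whole clinic, ages 2 to 18, so it is a proxy for ages 13 to 18.
- r = baseline-to-follow-up correlation. It is in no document and is varied over 0.5, 0.8, 0.9 and 0.95.
- Two-sided 5% level and 95% intervals: assumed.

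**1. Interval width.** The half-width is t × s × sqrt(2/n), with sqrt(2/40) = 0.2236.
- Follow-up value: s = 0.5, t(78 df) = 1.9908, so 1.9908 × 0.5 × 0.2236 = 0.223 at any r.
- Change: s = 0.5 × sqrt(2(1 − r)), t(78 df).
- ANCOVA: s = 0.5 × sqrt(1 − r²), t(77 df) = 1.9913, multiplied by sqrt(1 + 1/(2n − 4)) = sqrt(1 + 1/76) = 1.0066 to allow for chance baseline imbalance.

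| r | Follow-up | Change | ANCOVA | Narrower than follow-up by | Narrower than change by |
|---|---|---|---|---|---|
| 0.5 | 0.223 | 0.223 | 0.194 | 13% | 13% |
| 0.8 | 0.223 | 0.141 | 0.134 | 40% | 4.5% |
| 0.9 | 0.223 | 0.100 | 0.098 | 56% | 1.9% |
| 0.95 | 0.223 | 0.070 | 0.070 | 69% | 0.6% |

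The percentages are taken before rounding and do not depend on the SD. With 32 per arm (an assumed 20% loss) they are almost the same: 13% / 39% / 56% / 69% and 13% / 4.3% / 1.7% / 0.4%.

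**2. Gap between the two unadjusted estimates.** In the same participants, the follow-up difference minus the change difference equals the baseline difference between arms. Its SE is SD × sqrt(2/n) = 0.5 × 0.2236 = 0.112, whatever r is. For SD 0.3 to 0.6 it runs from 0.067 to 0.134.

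**3. Choice of response form at 6 months.** With no true effect, the follow-up and change statistics have correlation sqrt((1 − r)/2), which is 0.50 / 0.32 / 0.22 / 0.16 over the four values of r. By the bivariate normal, the chance that at least one has p < 0.05 is 9.1% / 9.5% / 9.6% / 9.7%. Simulation with t-tests (20,000 null trials per setting) gave 9.0% to 9.9%. A single named test has 5%.

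**The case against.** The strongest reply is that this is a pilot. Its aims are to finalise the intervention, to establish acceptability and feasibility, and to cost it. No efficacy hypothesis, alpha or power is stated, and no decision in the document turns on this contrast. That stands, and it limits the severity. It does not remove the point, because the sponsor typed BMI z-score as Primary and says that groups will be compared.

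A second reply is that change is the natural reading, since the protocol describes clinic results that way: "The children who are successful display a decrease in BMI z-score of 0.07 to 0.1". That sentence is background on the standard programme and does not bind the trial's analysis. If change is what the sponsor intends, though, the precision gain from ANCOVA is small, and most of the benefit comes from naming one analysis.

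Three stronger readings are tempting, and the documents do not support them.
- A reader might infer a false-positive rate of 14% to 17%. That range comes from counting five tests: value and change at 3 and 6 months, plus an arm-by-time ANOVA. It mixes the choice of response form with ordinary two-visit multiplicity, and the table already lists both visits. The figure for response form alone is 9% to 10%. It too shows the room the wording leaves and does not predict selective reporting.
- A reader might infer that intervals will be 40% to 69% wider than necessary. As reductions in width, those figures apply only if raw follow-up values are compared and r is 0.8 or more.
- A reader might set the gap between estimates against the 0.1 to 0.15 decrease that the protocol links with biomarker changes. That is a decrease in BMI z-score, not a margin between arms, so the gap is given here only as an SE.

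**Conclusion.** The point holds in a limited form. For the outcome typed Primary, the plan names a class of unadjusted tests and does not commit to using a baseline value it already collects. A named baseline-adjusted comparison is expected to be at least as precise at every r examined. The gain is 13% to 69% of interval width against raw follow-up values, and about 13% down to 0.6% against change scores. It also removes a choice between two estimates that differ by a quantity with SE 0.112.

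These sizes rest on 40 per arm, equal SDs, an assumed range of r and, for the 9% to 10%, an assumed 5% level. The SE of the gap also rests on the clinic-wide SD. A reader might infer that the trial misses its power or that a stated number is wrong. Neither follows, because the plan states no power and no such number. Nor does the change turn 40 per arm into an efficacy trial: at r = 0.8, power for a 0.10 difference is about 32% with adjustment, against 29% for change and 14% for the follow-up value. This is a free improvement of modest severity.

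**What to change.** Add one paragraph to the Analytical Plan. Youth BMI z-score at 6 months, the end of the treatment period, will be compared between arms as randomised by ANCOVA with baseline BMI z-score as covariate. The adjusted difference will be reported with its 95% CI. The 3-month value, analysed with the same model, and caregiver BMI will be secondary.

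The paragraph should commit to this one model and one visit. Offering alternatives, such as ANCOVA or a mixed model, would bring back the choice it is meant to close. If the sponsor prefers change scores, naming that analysis and the visit in advance would close most of the gap, with an interval that ANCOVA would have narrowed by about 0.6% to 13%.

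The cost is the wording and one residual degree of freedom (78 to 77; critical t 1.9908 to 1.9913). No participants, visits or measurements are added.
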